4.4.3. Method of Assigning Subjects to Treatment Groups (Randomization)

Enrollment/randomization was performed through the enrollment module of AdvantageEDC, the electronic data capture system maintained by the SDCC. The list of randomized treatment assignments was prepared by statisticians at the SDCC and included in the enrollment module for this trial. The electronic data capture system assigned each subject a treatment code after the demographic and eligibility data have been entered into the system. A designated individual at each site was provided with a treatment key, which links the treatment code to the actual treatment assignment, to be kept in a secure place.

At the time of consent and upon entry of demographic data and confirmation of eligibility for this trial, the subject is enrolled. In group 1 (5 mcg ZPIV, N=45; placebo, N=5), two sentinel subjects were enrolled first and received ZPIV in an open-label fashion. All other subjects were randomized in a double-blind fashion. Upon completion of enrollment in Group 1, Group 2 subjects (2.5 mcg ZPIV, N=35; placebo, N=5) were randomized. Subjects received the same study product at their first and second investigational vaccinations.

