6. GENERAL STATISTICAL CONSIDERATIONS

6.1. General Principles

All continuous variables will be summarized using the following descriptive statistics: n (non-missing sample size), mean, standard deviation, median, minimum and maximum, unless otherwise specified. The frequency and percentage of observed levels will be reported for all categorical measures; denominators for percentages will be defined for each analysis.

Listings will be provided for all data. Sort order will be specified on each listing shell in Appendix 3.

Summary tables will be structured with a column for each treatment group (2.5 mcg ZPIV, 5 mcg ZPIV, Placebo) and for all subjects for safety summaries.

All tables will be annotated with the total population size relevant to that table/group, including any missing observations.

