9.3. Adverse Events

When calculating the incidence of adverse events (i.e., on a per subject basis), each subject will only be counted once per AE using the event with maximum severity and any repetitions of adverse events within a subject will be ignored; the denominator will be the total treatment group size or the corresponding number of subjects receiving the second dose, as appropriate. All unsolicited adverse events reported will be included in [Listing 11](#).

An overall summary of adverse events from first administration of study vaccine to the end of the study is presented in [Table 36](#), [Table 37](#), and [Table 38](#) for all subjects, baseline flavivirus positive subjects and baseline flavivirus negative subjects, respectively.

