14.3 Safety Data

14.3.1 Displays of Adverse Events

Table 36: Overall Summary of Adverse Events – All Subjects

Event Category ^a	Subcategory	2.5 mcg ZPIV (N=X)		5 mcg ZPIV (N=X)		Placebo (N=X)		All Subjects (N=X)	
		n (%)	95% CI	n (%)	95% CI	n (%)	95% CI	n (%)	95% CI
At least one local solicited adverse event ^b		xx (xx)	xx.x, xx.x	xx (xx)	xx.x, xx.x	xx (xx)	xx.x, xx.x	xx (xx)	xx.x, xx.x
At least one systemic solicited adverse event ^b									
At least one unsolicited adverse event ^c									
At least one related unsolicited adverse event ^c	Any Severity								
	Mild (Grade 1)								
	Moderate (Grade 2)								
	Severe (Grade 3)								
At least one related laboratory adverse event ^c	Any Severity								
	Mild (Grade 1)								
	Moderate (Grade 2)								
	Severe (Grade 3)								
	Any Severity								
At least one related unsolicited or laboratory adverse event ^c	Mild (Grade 1)								
	Moderate (Grade 2)								
	Severe (Grade 3)								
	Any Relationship								
	Related								
At least one severe (Grade 3) unsolicited adverse event ^c	Unrelated								
At least one serious adverse event ^d									
At least one related serious adverse event ^d									
At least one adverse event leading to early termination from the study ^d									

Table 36: Overall Summary of Adverse Events -- All Subjects (continued)

Event Category ^a	Subcategory	2.5 mcg ZPIV (N=X)		5 mcg ZPIV (N=X)		Placebo (N=X)		All Subjects (N=X)	
		n (%)	95% CI	n (%)	95% CI	n (%)	95% CI	n (%)	95% CI
At least one adverse event leading to discontinuation of study product									
At least one adverse event of special interest (AESI) ^d									
At least one related AESI ^d									
At least one new onset chronic medical condition (NOCMC) ^d									
At least one related NOCMC ^d									

N = Number of subjects in the safety population. CI = Exact (Clopper-Pearson) confidence interval.
n = Number of subjects experiencing the event.

^a Subjects are counted once for each category regardless of the number of events.
^b Solicited AEs are collected through Day 8 post each dose.
^c Non-serious unsolicited AEs within 28 days of either dose.
^d At any time during the study.

Tables with similar format:

Table 37: Overall Summary of Adverse Events – Baseline ZIKV Seropositive Subjects

[Implementation note: N = Number of subjects in the Safety population with specified baseline flavivirus immune status]

Table 38: Overall Summary of Adverse Events – Baseline ZIKV Seronegative Subjects

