Baseline ZIKV Seronegative and DENV Seropositive (N* = X)															
Baseline ZIKV Seronegative and DENV Seronegative (N* = X)															

N = Number of subjects in the Safety Population who received the specified dose; N* = Number of subjects in the Safety population with the specified baseline flavivirus immune status, used as denominator for percentages; n=Number of subjects reporting an event under the SOC and PT combination; m = Number of events under the SOC and PT combination.

Post dose columns include events reported within 28 days following the dose; Post-Any Dose column includes events reported within 28 days following either dose.

95% CI = 95% exact Clopper-Pearson confidence interval

Tables with similar format:

Table 133: Number and Percentage of Subjects Experiencing Unsolicited Adverse Events by MedDRA System Organ Class, Preferred Term, Severity, Dose, and Baseline Flavivirus Immune Status – 5 mcg ZPIV

Table 134: Number and Percentage of Subjects Experiencing Unsolicited Adverse Events by MedDRA System Organ Class, Preferred Term, Severity, Dose, and Baseline Flavivirus Immune Status – Placebo

Table 135: Number and Percentage of Subjects Reporting NOCMCs by MedDRA System Organ Class, Preferred Term, Treatment Group, and Baseline Flavivirus Immune Status

Baseline Flavivirus Immune Status	MedDRA System Organ Class	MedDRA Preferred Term	2.5 mcg ZPIV (N=X)				5 mcg ZPIV (N=X)				Placebo (N=X)				All Subjects (N=X)			
			n	%	95 % CI	m	n	%	95 % CI	m	n	%	95 % CI	m	n	%	95 % CI	m
All Subjects (N* = X)	Any SOC	Any PT	x	xx	xx.x, xx.x	x	x	xx	xx.x, xx.x	x	x	xx	xx.x, xx.x	x	x	xx	xx.x, xx.x	x
	[SOC 1]	Any PT																
		[PT 1]																
		[PT 2]																
	[SOC 2]	Any PT																
		[PT 1]																
		[PT 2]																
Repeat for:																		
Baseline ZIKV Seropositive (N* = X)																		
Baseline ZIKV Seronegative (N* = X)																		
Baseline ZIKV Seropositive and DENV Seropositive (N* = X)																		
Baseline ZIKV Seropositive and DENV Seronegative (N* = X)																		
Baseline ZIKV Seronegative and DENV Seropositive (N* = X)																		
Baseline ZIKV Seronegative and DENV Seronegative (N* = X)																		

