N = Number of subjects in the Safety population; N* = Number of subjects in the Safety population with the specified baseline flavivirus immune status used as the denominator for percentages; n = Number of subjects reporting an event under the SOC and PT combination; m = Number of events under the SOC and PT combination. Table includes events reported from time of first administration of study vaccine through 28 days after the last vaccination.																		

Table with similar format:

Table 136: Number and Percentage of Subjects Reporting AESIs Related to Study Treatment by MedDRA System Organ Class, Preferred Term, Treatment Group, and Baseline Flavivirus Immune Status

Table 137: Duration (Days) of AESIs Related to Study Treatment by MedDRA System Organ Class, Preferred Term, Treatment Group, and Baseline Flavivirus Immune Status

Baseline Flavivirus Immune Status	MedDRA System Organ Class	MedDRA Preferred Term	Statistic	2.5 mcg ZPIV (N=X)	5 mcg ZPIV (N=X)	Placebo (N=X)	All Subjects (N=X)
All Subjects (N*=X)	Any SOC	Any PT	n	x	x	x	x
			Mean (SD)	x.x (x.x)	x.x (x.x)	x.x (x.x)	x.x (x.x)
			Median	x.x	x.x	x.x	x.x
			Min, Max	x, x	x, x	x, x	x, x
		[PT 1]	n				
			Mean (SD)				
			Median				
			Min, Max				
	[SOC 1]	Any PT	n				
			Mean (SD)				
			Median				
			Min, Max				
		[PT 1]	n				
			Mean (SD)				
			Median				
			Min, Max				
	[SOC 2]	Any PT	n				
			Mean (SD)				
			Median				
			Min, Max				
		[PT 1]	n				
			Mean (SD)				
			Median				
			Min, Max				

Table 137: Duration (Days) of AESIs Related to Study Treatment by MedDRA System Organ Class, Preferred Term, Treatment Group, and Baseline Flavivirus Immune Status (continued)

Baseline Flavivirus Immune Status	MedDRA System Organ Class	MedDRA Preferred Term	Statistic	2.5 mcg ZPIV (N=X)	5 mcg ZPIV (N=X)	Placebo (N=X)	All Subjects (N=X)
Repeat for:							
Baseline ZIKV Seropositive (N* = X)							
Baseline ZIKV Seronegative (N* = X)							
Baseline ZIKV Seropositive and DENV Seropositive (N* = X)							
Baseline ZIKV Seropositive and DENV Seronegative (N* = X)							
Baseline ZIKV Seronegative and DENV Seropositive (N* = X)							
Baseline ZIKV Seronegative and DENV Seronegative (N* = X)							
N = Number of subjects in the Safety population; N* = Number of subjects in the Safety population with the specified flavivirus status used as the denominator for percentages; n = number of subjects reporting an AESI related to study treatment							

Table with similar format to Table 110:

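### SAP Tables 135 and 136 show treatment arms as columns but name a serostatus-only row total as the percentage denominator, in conflict with SAP 9.3

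*SAP*

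**What the plan says.** SAP 6.1 sets the general layout: "Summary tables will be structured with a column for each treatment group (2.5 mcg ZPIV, 5 mcg ZPIV, Placebo"), with an added column for all subjects in safety summaries. Table 135 follows it, and each column is headed by its own N. The row blocks are the serostatus groups, and each block carries one further count, for example "Baseline ZIKV Seropositive (N* = X"). The footnote defines N as the Safety population and then makes the other symbol the divisor: "N* = Number of subjects in the Safety population with the specified baseline flavivirus immune status used as the denominator for percentages". Table 136 is declared to have a similar format.

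Two other places bear on the same percentages. SAP 9.3 says of adverse event incidence that "the denominator will be the total treatment group size or the corresponding number of subjects receiving the second dose, as appropriate". Table 36, which has rows for any related SAE, any related AESI and any new-onset chronic condition, uses the column count: "N = Number of subjects in the safety population. CI = Exact (Clopper-Pearson) confidence interval". Tables 37-42 repeat it one stratum at a time, with the column N restricted to that serostatus.

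Table 138 (related SAEs) is introduced only as "Table with similar format to Table 110". Table 110 is a placebo table of solicited events by day.

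**The concern.** A per-arm percentage needs a per-arm denominator. N* in Table 135 names no arm and is printed once per row block, so a programmer who follows the footnote divides the 2.5 mcg, 5 mcg and placebo counts by the same number. That number is right only for the All Subjects column. The resulting percentages rise with arm size, and placebo is by far the smallest arm.

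The likely origin is carry-over. Tables 129-131 use nearly the same footnote, but each of those tables holds a single arm, so N* there is naturally the stratum within that arm. In Table 135 the arms became columns and the footnote was not adapted.

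At stake are the SOC/PT summaries by arm and serostatus for primary endpoint 4 (new-onset chronic conditions) and for the AESI part of primary endpoint 3. As written they could suggest a vaccine excess where none exists, give placebo intervals that are far too narrow, and disagree with the matching rows of Table 36 in the same report.

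**Working it through.** **Inputs.** SAP 4.4.3: "In group 1 (5 mcg ZPIV, N=45; placebo, N=5") and "Group 2 subjects (2.5 mcg ZPIV, N=35; placebo, N=5) were randomized". SAP 6.1 pools placebo into one column.

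**Arm sizes.** 2.5 mcg: 35. 5 mcg: 45. Placebo: 5 + 5 = 10. Total: 35 + 45 + 10 = 90.

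**The plan's own figures.** ZPIV recipients are 45 + 35 = 80, as in SAP Section 5. SAP Table 8 reproduces: 1 - 0.98^80 = 80.1% and 1 - 0.95^35 = 83.4%. The SAP gives no figure for the Table 135 percentages.

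**Effect of the literal denominator, All Subjects block.** For a true risk p equal in all arms, the expected display is (arm size × p)/90 instead of (arm size × p)/(arm size). Each rate is too small by 90/35 = 2.6, 90/45 = 2.0 and 90/10 = 9.0. The ratios to placebo are 35/10 = 3.5 and 45/10 = 4.5, whatever p is. Placebo could never exceed 10/90 = 11.1%.

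**Illustration at an assumed 20% in every arm** (the documents give no rate), with exact 95% intervals:

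| Arm | Count | Arm denominator | Denominator 90 |
|---|---|---|---|
| 2.5 mcg | 7 | 20.0% (8.4-36.9) | 7.8% (3.2-15.4) |
| 5 mcg | 9 | 20.0% (9.6-34.6) | 10.0% (4.7-18.1) |
| Placebo | 2 | 20.0% (2.5-55.6) | 2.2% (0.3-7.8) |

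At an assumed 10%, the expected displays are 3.9%, 5.0% and 1.1%.

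**Zero placebo events.** The exact upper limit is 1 - 0.025^(1/n): 30.8% for n = 10 and 4.0% for n = 90.

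**Serostatus blocks.** Here the ratio is the arm's count in the stratum over placebo's count in the stratum, and the documents do not give the split. As a range, strata were drawn at random from the 90, keeping draws with at least two placebo subjects. The 5th to 95th percentiles of the ratio to placebo were:

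| Stratum size (assumed) | 2.5 mcg | 5 mcg |
|---|---|---|
| 18 | 1.0-4.5 | 1.5-5.5 |
| 45 | 2.0-7.0 | 2.7-8.7 |
| 72 | 2.7-5.0 | 3.5-6.3 |

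**Does SAP 9.3 supply the right number?** In the All Subjects block, yes: treatment group size is the correct divisor. In a serostatus block it is not. If a fraction f of an arm belongs to the stratum, dividing by the whole arm multiplies the true stratum rate by f. The shell prints the arm total (column N) and the stratum total (row N*), but nowhere the count of subjects in both.

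**The case against.** The strongest reply is that the SAP never says the denominator runs over all arms. Near-identical wording under arm columns in Tables 37-42 and 46-51 can only mean the stratum within the arm, so house style may let the column supply the arm. SAP 9.3 gives treatment group size, and SAP 9.4 asks for these percentages by treatment group and serostatus. The footnote is also visibly boilerplate: Table 137 carries the same denominator phrase although it shows durations and no percentages. N* is loose elsewhere too. In Tables 132-134 one row-level N* spans dose columns that have their own N, whereas SAP 9.3 calls for second-dose recipients.

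Much of this stands. A careful programmer might well compute the right figures, and the SAP is better described as inconsistent than as settled on a wrong rule. The reply does not remove the fault. In Tables 37-42 the restricted count sits in each arm's column; in Table 135 it sits in the row, beside a separate column N that the footnote passes over. SAP 9.3 is also wrong inside the serostatus blocks.

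The reach is limited as well. Tables 36-42 give any-event rates for new-onset chronic conditions, related AESIs and related SAEs by arm and serostatus on column N. Tables 189 and 191 list the individual events. With n and the arm N printed, a reader can recompute the All Subjects rates in Table 135. The 20% risk is illustrative and would be high for related AESIs, since Protocol 9.5.3 halts the study for SMC review after a single related SAE or AESI.

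**Conclusion.** The point holds for Tables 135 and 136. Their stated denominator, followed literally, is the stratum total over all arms; it conflicts with SAP 9.3 and would not agree with Tables 36-42. The ratios of 3.5 and 4.5, and the 4.0% limit in place of 30.8%, assume the planned arm sizes and apply to the All Subjects block.

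A reader might infer three stronger things that the documents do not support:

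- **That all arm rates for primary endpoints 3 and 4 are wrong.** They are not: the any-event rates in Tables 36-42 use column N, and the fault lies only in the SOC/PT tables.
- **That 3.5 and 4.5 apply in every serostatus stratum.** The split is not given, so no single figure can be stated there.
- **That Table 138 shares the fault.** Its layout is unspecified because its pointer is stale. That it was meant to follow Table 135 is an inference from its title.

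This should be corrected before the final tables are programmed. It does not affect the design or the data collected.

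**What to change.** In the footnote of Table 135, define N* as the number of Safety subjects in that treatment group (column) with the specified baseline serostatus. Print it for each arm and each stratum, and base the percentages and Clopper-Pearson intervals on it. The All Subjects column keeps the total over arms. Apply the same to Table 136.

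Repair the format pointers: Table 138 to the corrected Table 135 instead of Table 110, and Table 139 to Table 137 instead of Table 111.

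Check two further places where N* sits at row level: Tables 132-134, where the post-dose 2 columns need second-dose recipients under SAP 9.3, and Table 168, where N* is set by infection confirmation status while the arms are columns.

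The cost is footnote and shell wording. No new data are needed.

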## **3.2 Study Outcome Measures**

### **3.2.1 Primary Endpoints**

#### Safety and Reactogenicity:

1. Frequency and severity of solicited injection site and systemic reactogenicity from time of study vaccine administration through Day 8 after each administration of study vaccine overall and by dosage group and pre-vaccination flavivirus immune status.
2. Frequency and severity of unsolicited vaccine-related adverse events (AE), including vaccine-related laboratory AE, from first administration of study vaccine until 28 days after the last vaccination overall and by dosage group and pre-vaccination flavivirus immune status.
3. Frequency, type, and duration of serious adverse events (SAE) and adverse events of special interest (AESI) considered related to study vaccine from the first administration of study vaccine until the end of the study overall, and by dosage group and pre-vaccination flavivirus immune status.
4. Frequency of new onset chronic medical conditions reported at any time from the first administration of study vaccine until the end of the study overall, and by dosage group and pre-vaccination flavivirus immune status.
5. Comparison of the frequency, type, and duration of vaccine-related Grade 3 local, systemic, or laboratory AE, and Grade 2 or greater local or systemic reactogenicity through Day 8 after each study vaccine administration between dosage groups and by pre-vaccination flavivirus immune status.
6. Comparison of study withdrawals and discontinuation of study vaccination due to any reason between dosage groups and by pre-vaccination flavivirus immune status.

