## **9.4 Type and Duration of Follow-up of Adverse Events**

Solicited injection site and systemic AEs (reactogenicity events) will be documented and reported from Day 1 through Day 8 after each study vaccination via memory aid, clinic visits on Day 2 and Day 8 after vaccination, and interview by telephone visit on Day 4 after each study vaccination.

Unsolicited AE will be documented from Day 1 through approximately 28 days after the last vaccination. Blood for safety laboratory tests will be collected on Day 8 and Day 15 after each study vaccination. All AEs will be assessed and followed through resolution or stabilization even if this extends beyond the study-reporting period.

AEs related to AFI/ARI will be collected and assessed from the time the ICF is signed through the end of the study, and followed until resolution or stabilization.

SAE, AESIs, and new-onset chronic medical conditions will be collected and assessed from the time of the first study vaccination through the end of the study, and followed until resolution or stabilization. Resolution of an AE and SAE is defined as the return to pretreatment status or stabilization of the condition with the expectation that it will remain chronic.

AFI and ARI will be collected after signing ICF through the end of the study.

Follow-up procedures, evaluations, and outcomes will be recorded on the appropriate case report form.

---

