3.2. Endpoints

Primary Endpoints:

1. Frequency and severity of solicited injection site and systemic reactogenicity from time of study vaccine administration through Day 8 after each administration of study vaccine overall and by dosage group and pre-vaccination flavivirus immune status.
2. Frequency and severity of unsolicited vaccine-related adverse events (AE), including vaccine-related laboratory AE, from first administration of study vaccine until 28 days after the last vaccination overall and by dosage group and pre-vaccination flavivirus immune status.
3. Frequency, type, and duration of serious adverse events (SAE) and adverse events of special interest (AESI) considered related to study vaccine from the first administration of study vaccine until the end of the study overall, and by dosage group and pre-vaccination flavivirus immune status.
4. Frequency of new onset chronic medical conditions reported at any time from the first administration of study vaccine until the end of the study overall, and by dosage group and pre-vaccination flavivirus immune status.
5. Comparison of the frequency, type and duration of vaccine-related Grade 3 local, systemic, or laboratory AE, and Grade 2 or greater local or systemic reactogenicity through Day 8 after each

study vaccine administration between dosage groups and by pre-vaccination flavivirus immune status.

6. Comparison of study withdrawals and discontinuation of study vaccination due to any reason between dosage groups and by pre-vaccination flavivirus immune status.

Secondary Endpoints:

1. Frequency of seroconversion to ZIKV at each post-vaccination visit measured by ZIKV ELISA and neutralization assay in comparison with baseline samples (collected at Visit 00) overall, and by dosage group and pre-vaccination flavivirus immune status.
2. Per Visit GMT as measured by ZIKV ELISA and neutralization assay after each study vaccine administration and for each post-vaccination visit overall, and by dosage group and pre-vaccination flavivirus immune status.
3. Peak GMT as measured by ZIKV ELISA and neutralization assay after each vaccination and overall, and by dosage group and pre-vaccination flavivirus immune status.
4. Proportion of subjects with at least a 4-fold rise in ZIKV GMT as measured by ZIKV ELISA and neutralization assay at 4 weeks after each vaccination compared with baseline overall, and by dosage group and pre-vaccination flavivirus immune status.

Exploratory Endpoints:

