Venous blood and urine were collected from subjects on Day 8 and Day 15 following each vaccination for safety clinical laboratory tests. The tests include WBC, hemoglobin, hematocrit, and platelets, ALT, AST, total bilirubin, BUN, creatinine, and urine dipstick for protein and glucose. Laboratory values were assessed for adverse events according to the grading scale in [Table 7](#). Unsolicited adverse events were collected from all subjects through Day 57 (28 days after the 2nd vaccination). These events were assessed for severity and relatedness to study product. Serious adverse events (SAE), adverse events of special interest (AESI), and new onset chronic medical conditions (NOCMC) were collected for the duration of each subject's follow-up. Adverse events of special interest (AESI) for this study are neurologic and neuroinflammatory disorders collected through the duration of the subject's follow-up period.

Subjects were observed for development of an AFI/AI and all related adverse events from the time of signing the informed consent form through follow-up. Subjects who reported an ARI/AI were assessed for the following symptoms which are graded on a scale from 1 (least severe) to 3 (most severe): fever, feverishness, lethargy, restlessness, rash not at injection site, nonpurulent conjunctivitis, headache, shortness of breath, retino-orbital pain, myalgia, arthralgia, arthritis, nausea, abdominal pain, vomiting (evaluated for presence only), and bleeding (evaluated for presence only).

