9.4. Deaths, Serious Adverse Events and other Significant Adverse Events

Serious adverse events including deaths will be listed in [Table 189](#). A listing of AESIs and NOCMCs will be presented in [Table 191](#).

The number and percentage of subjects reporting new onset chronic medical conditions is summarized by MedDRA SOC and PT by treatment group and baseline flavivirus immune status in [Table 135](#).

Similar summaries for the number and percentage of subjects reporting AESIs related to study treatment are presented in [Table 136](#). The duration in days of AESIs is summarized in [Table 137](#).

Summaries of the number of subjects reporting serious adverse events related to study treatment are available in [Table 138](#). The duration in days of the related SAEs is summarized in [Table 139](#).

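### The Table 135 footnote cuts the summary of new-onset chronic medical conditions at 28 days after the last dose, although primary endpoint 4 runs to the end of the study

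*SAP*

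**What the plan says.** **Endpoint.** Primary endpoint 4 (protocol section 3.2.1, repeated in SAP section 3.2) is worded: "Frequency of new onset chronic medical conditions reported at any time from the first administration of study vaccine until the end of the study". It is to be shown pooled, by dose arm and by serostatus.

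**Collection.** Protocol section 9.4 states that "new-onset chronic medical conditions will be collected and assessed from the time of the first study vaccination through the end of the study". SAP section 4.5 agrees, the period being a subject's whole follow-up: "new onset chronic medical conditions (NOCMC) were collected for the duration of each".

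**Analysis text.** SAP section 9.4 says: "The number and percentage of subjects reporting new onset chronic medical conditions is summarized by MedDRA SOC and PT". The display named is Table 135, split by arm and serostatus. The text gives no time limit, and neither does the table title.

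**Table shell.** The Table 135 footnote in SAP Appendix 1 says: "Table includes events reported from time of first administration of study vaccine through 28 days after the last vaccination".

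**Overall summary.** SAP section 9.3 introduces Tables 36 to 38 with: "An overall summary of adverse events from first administration of study vaccine to the end of the study is presented in". The first of these has a row for subjects with at least one NOCMC, under footnote d: "At any time during the study". Tables 37-42 repeat that format for the two ZIKV strata and the four ZIKV/DENV strata.

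**Related shell.** Table 136 (related adverse events of special interest, AESIs) is given only as having the format of Table 135. Its endpoint, primary endpoint 3, covers "adverse events of special interest (AESI) considered related to study vaccine from the first administration of study vaccine until the end of the study".

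**The concern.** The footnote contradicts the endpoint, the collection period and the SAP text that calls for the table. The 28-day limit is the correct window for non-serious unsolicited adverse events, and nearly the same sentence stands under Table 129, where it belongs. It was probably carried over from there, though that is an inference. SAP section 15, which lists changes to the planned analyses, does not mention a shorter window for NOCMCs, so nothing suggests a deliberate choice.

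Three things are at stake:

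- Table 135 is the only planned summary of NOCMCs by SOC and PT, and the only one with event counts. As written it uses no report from the 12 scheduled visits after Day 57 (Visits 12 to 23).
- Its row for any SOC and any PT shares treatment columns and serostatus strata with the NOCMC row of Tables 36-42, but not the window. The two counts can differ for the same arm.
- If the footnote travels with the format to Table 136, the related-AESI summary would also stop early, against endpoint 3. The SAP does not say whether it does.

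**Working it through.** **1. Day counts, from the documents**

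- Second dose on Day 29, so 28 days later is 29 + 28 = Day 57. SAP section 4.5 gives the same day.
- Last visit is Day 722 counted from the second dose: 29 + 722 - 1 = Day 750. Protocol section 8.4.1 gives the same day.
- Planned time covered by Table 135: (57 - 1)/(750 - 1) = 56/749 = 7.5%. Omitted: 749 - 56 = 693 days.
- Across visit windows (Day 57 ± 3, Day 750 ± 14): from (54 - 1)/(764 - 1) = 53/763 = 6.9% to (60 - 1)/(736 - 1) = 59/735 = 8.0%.
- For a subject with only one dose: 28/749 = 3.7%.

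**2. How often the two tables would disagree (illustration)**

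Column sizes come from SAP section 4.4.3: 2.5 mcg N = 35; 5 mcg N = 45; placebo N = 5 + 5 = 10; all subjects N = 90. The documents give no NOCMC rate. I assume a 24-month risk *p* of 2%, 5%, 10% or 20%, constant hazard, two doses and complete follow-up.

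- Risk inside the Table 135 window: q = 1 - (1 - p)^(56/749).
- Expected subjects: N × p in Table 36, N × q in Table 135.
- The rows differ if at least one subject has a first NOCMC after the window: 1 - (1 - (p - q))^N.

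Example, p = 0.05 and N = 35: q = 1 - 0.95^(56/749) = 0.00383. Expected subjects are 35 × 0.05 = 1.75 and 35 × 0.00383 = 0.13. The chance of disagreement is 1 - (1 - 0.04617)^35 = 0.81.

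| Column | Quantity | p = 2% | 5% | 10% | 20% |
|---|---|---|---|---|---|
| 2.5 mcg, N = 35 | Expected, Table 36 | 0.7 | 1.75 | 3.5 | 7 |
| | Expected, Table 135 | 0.05 | 0.13 | 0.28 | 0.58 |
| | Chance rows differ | 48% | 81% | 97% | 99.9% |
| 5 mcg, N = 45 | Expected, Table 36 | 0.9 | 2.25 | 4.5 | 9 |
| | Expected, Table 135 | 0.07 | 0.17 | 0.35 | 0.75 |
| | Chance rows differ | 57% | 88% | 99% | >99.9% |
| Placebo, N = 10 | Chance rows differ | 17% | 38% | 62% | 87% |
| All subjects, N = 90 | Expected, Table 36 | 1.8 | 4.5 | 9 | 18 |
| | Expected, Table 135 | 0.14 | 0.34 | 0.71 | 1.49 |
| | Chance rows differ | 81% | 99% | >99.9% | >99.9% |

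In the 2.5 mcg, 5 mcg and all-subjects columns, replacing 56/749 by the visit-window extremes moves the disagreement figures by at most 0.003.

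**3. Where a late NOCMC could still be found**

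- Table 191 lists AESIs and NOCMCs with the event term, an NOCMC flag and the SOC, but no PT.
- Listing 11 carries SOC and PT but no NOCMC flag, so it would have to be matched to Table 191. SAP section 4.5 says unsolicited events were collected through Day 57, and it is not stated that a late, non-serious NOCMC appears in this listing.
- If the condition is also an SAE, Table 189 shows it with SOC and PT at any time in the study.
- If it is a related AESI (multiple sclerosis and narcolepsy are on the AESI list) or a related SAE, it could appear by SOC and PT in Table 136 or Table 138.

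**The case against.** The strongest reply is that this is one line in a mock-up, contradicted by the body of the SAP. The frequency that endpoint 4 asks for is reported for the whole study in Tables 36-42, no data are lost and no test is affected. Both tables print their window, so a reader who sees two counts can see why. Table 191 lists every NOCMC by term and SOC, which in a 90-subject trial goes most of the way. The disagreement probabilities rest on assumed risks, and they fall in smaller cells such as placebo.

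Most of this stands, and it is why the point is not graded higher. It does not remove the problem. Programmers work from shells, and this one tells them to apply a date filter that the SAP text does not support. A printed window explains a difference but does not make the window right for a primary endpoint. Tables 36-42 give neither the SOC/PT breakdown nor event counts. The 56 of 749 days rests on no assumed rate.

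One caveat on Tables 37-42: SAP section 6.4 confines immune-status subgroups to secondary and exploratory endpoints and suppresses strata with fewer than two subjects. That conflicts with these shells and with endpoint 4, and needs its own reconciliation.

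**Conclusion.** The concern holds. The Table 135 footnote is wrong as written: it covers 7.5% of planned follow-up (6.9% to 8.0% across visit windows), whereas the endpoint, the collection period and SAP section 9.4 all call for the whole study. The consequence is a truncated SOC/PT summary and a probable mismatch with Tables 36-42. The primary endpoint itself is not lost. The contradiction and the day counts come straight from the documents and are firm. The mismatch probabilities are illustrations that depend on the assumed 24-month risks, constant hazard, two doses and complete follow-up. For Table 136 the finding is only that its window is unstated. It should be fixed before the final tables are produced.

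**What to change.** - Change the Table 135 footnote so that the window runs from the first vaccination to the end of the study.
- State the same window on Tables 136, 137, 138 and 139.
- Correct two cross-references (editorial). Tables 138 and 139 point to Tables 110 and 111, which are solicited-reaction tables. Table 138 should follow the Table 135/136 format and Table 139 the Table 137 format. Their titles and SAP section 9.4 already fix their content.
- Add a programming check that the number of subjects in the any-SOC, any-PT row of Table 135 equals the NOCMC row of Tables 36-42, for each treatment column and each serostatus stratum that is produced.

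The cost is one footnote, a window statement on four shells, two cross-references and one date filter. No new data are required.
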